The rabies mortality from bites to the head by the same rabid wolf in Iran in 1955 was 3/5 (60%) in subjects receiving rabies vaccine alone. The mortality fell to 1/12 (8%) when both rabies vaccination and rabies antisera were administered (Baltazard et al.1955). A study by the same group from 1974 found that a rabies vaccine from human diploid cells combined with mule-derived anti-rabies antiserum yielded 0% rabies mortality in 44 bitten individuals without disease manifestations even with delays of up to 14 days (Bahmanyar et al.1976). Delays of up to 4 days in the initiation of rabies immune globulin after anti-rabies vaccination have demonstrated no inhibition of anti-rabies activity in blood (Khawplod et al.1996). There is some inhibition of the immune response to rabies vaccination by rabies immune globulin itself that has been recognized since early experience (Loofbourrow et al. 1971, Hattwick et al.1974, Vodopija et al. 1988). The inhibition of immune response by RIG varied in a range generally accepted as adequate. There has not been a single case of rabies in an individual receiving proper PEP in the United States since 1980. The combination of rabies vaccine with rabies immune globulin (RIG) has continued to be used and remains the standard of care despite inhibition of rabies vaccine immune response (Manning et al. 2008, Kedrab, 2017).

The passive administration of RIG is intended to provide an immediate supply of virus neutralizing antibodies to bridge the gap until the induction of active immunity in response to rabies vaccine administration. The use of RIG provides rapid passive immunity that persists for a short time (half-life of approximately 21 days) (Manning et al. 2008). There is sometimes an interaction between RIG and the immune response elicited by the rabies vaccine thus the dose of

rabies immune globulin must be evaluated to ensure no significant inhibition (Vodopija et al.1988b).

Three anti-rabies immunoglobulin formulations prepared from hyperimmunized human donors have been approved by the FDA: HyperRab® S/D (Grifols Therapeutics) and Imogam® Rabies- HT (Sanofi Pasteur) and Kedrab® (Kamada Ltd.). Since all HRIG preparations are considered equivalent HyperRab® S/D will be used as the HRIG in this trial.

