Rabies virus may gain access to the brain within approximately 30 hours from a jaw injection (Shankar et al. 1991). Anti-rabies Mabs can interrupt this process (Schumacher et al. 1989). It is difficult to pinpoint the exact interval from studies reporting days since the counting of days may use different conventions. The interval chosen for this protocol is 48 hours plus 6 hours (54 hours) that would permit PEP to start on the third day after the bite but more likely 48 hours from the bite assuming that most bites and their PEP will occur in the daytime.

Rationale for blinding

The pharmacy will be unblinded in this study because of the need to draw up the dose based on patient weight. Since weights will be different the different volumes will not disclose identity and it will be necessary to visually blind the syringes with tubes because of slight differences in the appearance of the Study Drugs. Nevertheless it will be difficult to have absolute blinding

with HRIG. Synermore judges that since the elements of the endpoint are objective the importance of blinding weaknesses in this study is secondary to adequate objective controls.

Rationale for NRG follow-up period

When the exposure time is known the incubation period of most cases occurs between 46-189 days (Noah et al. 1998, Quiambao et al. 2009, Ren et al. 2015,) Some rabies incubation periods are more than a year (Boland et al. 2014). A six month follow-up will capture most cases but follow up for a year should capture almost all cases of rabies.

Rationale for interval for avoidance of pregnancy

SYN023 and HRIG are both immunoglobulins. SYN023 is not detectable in the blood by Study Day 99. Study Day 121 will be over 5 half-lives from administration and SYN023 should be eliminated from the circulation thus prohibition of pregnancy for the rest of the trial cannot be based on SYN023 exposure.

Rationale for route of administration

Immune globulins are administered by direct injection into the wound or by subcutaneous or intramuscular injection when this is not possible. Direct injection into the wound has been associated with good outcomes whereas injection at remote sites has been associated with failure of PEP (Wilde et al. 1996, Wilde et al. 1992, Shantavsinkul et al. 2010, Hemachudha et al. 1999, Bharti et al. 2016)

Rationale for SYN023 dose level

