9.4. Physical Examination

Summaries for physical exam results on the As-treated Population including shifts will be provided following the same presentation for categorical clinical laboratory tests.

10. Pharmacokinetics

To describe the pharmacokinetics of SYN023 using non-compartmental analysis, V_d , C_{max} , T_{max} , AUC_{1-t} , AUC_{1-inf} , $t_{1/2}$, Cl , and λ_z will be calculated, when possible, in the LRG and NRG Per-protocol and As-treated Populations.

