10.2. Pharmacokinetic Concentrations

Blood samples will be obtained during the course of the study for use in determining the PK concentrations of CTB011 and CTB012 in serum. These will be collected before administration of study drug on Study Day 1 for all subjects, then on Study Days 4, 8, 15, 29, 43, 71, 127, 155, 183 and 274 for the LRG; and on Study Days 4, 8, 15 and 99 for the NRG.

Individual serum concentrations of CTB011 and CTB012 will be presented in the data listings and summarized by nominal time point for ease of presentation using descriptive statistics (n , mean, SD, CV, min, median, and max), by ADA status, and also by Per-protocol (LRG and NRG) and As-treated Populations. The mean serum concentrations of CTB011 and CTB012 will be plotted versus nominal collection time, and the individual serum concentration of CTB011 and CTB012 will be plotted versus actual collection time on both linear and semilogarithmic scales, by ADA status.

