10.3. Pharmacokinetic Parameters

The serum concentration-time data for CTB011 and CTB012 will be analyzed by non-compartmental analysis using WinNonlin Phoenix Version 8.0 or higher. For PK analysis, actual sampling times and actual doses administered will be used. For the calculation of PK parameters, all serum concentrations that are BLQ prior to the first measurable concentration will be set to zero. The BLQ values that are between measurable concentrations will be set to missing. The BLQ values that occur at the end of the profile after the last quantifiable concentration will be set to missing.

If data allow, the following PK parameters will be derived from the individual serum concentrations of CTB011 and CTB012 over time profile using non-compartmental methods:

AUC _{1-t}	Area under the serum concentration-time curve from time 0 on Study Day 1 to the last quantifiable concentration, calculated using the linear trapezoidal linear interpolation rule
AUC _{1-inf}	Area under the serum concentration-time curve from time 0 on Study Day 1 extrapolated to infinity, calculated using the formula: AUC _{1-inf} = AUC _{1-t} + [C _t / λ _z], where C _t is the last measurable serum concentration and λ _z is the terminal elimination rate constant. If the extrapolated area (C _t /λ _z) is greater than 20% of AUC _{1-inf} , then AUC _{1-inf} and its associated parameters (CL/F and Vd/F) will be set to missing.
C _{max}	Maximum observed serum concentration
T _{max}	Time of maximum observed serum concentration
λ _z	Terminal elimination rate constant, where λ _z is the magnitude of the slope of the linear regression of the log concentration versus time profile during the terminal phase. λ _z will only be retained if R ² ≥ 0.80 and 3 points in the terminal phase that do not include C _{max} are included in determining the regression line.
t _{1/2}	Terminal half-life (whenever possible), calculated as ln(2)/λ _z
CL/F	Apparent clearance, calculated as Dose/AUC _{1-inf}
Vd/F	Apparent volume of distribution, calculated as (CL/F)/λ _z

Individual serum PK parameters of CTB011 and CTB012 will be presented in the data listings. Further, CTB011 and CTB012 PK parameters will be summarized using descriptive statistics (n, mean, SD, CV, min, median, and max) by ADA status, and also by Per-protocol (LRG and NRG) and As-treated Populations.

11. Pharmacodynamics

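### NRG sampling of SYN023 on Days 4, 8, 15 and 99 cannot support the SAP's terminal-phase rule in any subject below quantification at Day 99, so half-life, AUC1-inf, CL/F and Vd/F would come only from a selected subset

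*SAP*

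**What the plan says.** SAP Section 10 says that Vd, Cmax, Tmax, AUC1-t, AUC1-inf, half-life, clearance and λz "will be calculated, when possible, in the LRG and NRG Per-protocol and As-treated Populations". SAP 10.2 sets the sampling: "These will be collected before administration of study drug on Study Day 1 for all subjects", and then "on Study Days 4, 8, 15 and 99 for the NRG". Protocol Appendices C and D give the same NRG days.

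SAP 10.3 adds four rules that matter here:

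- λz is kept only if R² is at least 0.80 and there are "3 points in the terminal phase that do not include" Cmax.
- "The BLQ values that occur at the end of the profile after the last quantifiable concentration will be set to missing".
- AUC1-t runs to the last quantifiable concentration by linear trapezoid. If more than 20% of AUC1-inf is extrapolated, then AUC1-inf, CL/F and Vd/F are set to missing.
- Half-life, AUC1-inf, CL/F and Vd/F are all computed from λz.

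Protocol 1.6 states that "SYN023 is not detectable in the blood by Study Day 99". Protocol 7.3 is softer and says only that most of the administered antibody will have gone by then. No SYN023 half-life and no assay limit is given. The one half-life stated, in Protocol 1.1, is a "half-life of approximately 21 days" for rabies immune globulin.

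**The concern.** The NRG schedule and the λz rule do not fit together. The Day 1 sample is pre-dose and cannot enter a log-linear terminal fit, so each NRG profile has four usable samples at most, and the last is one the protocol expects to be unmeasurable. If it is, the three-point rule cannot be met.

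The qualifier that parameters are derived where the data allow does not cure this. It keeps whoever happens to pass, and passing depends on the quantity being estimated, since a subject with slow elimination is more likely to be quantifiable at Day 99. The NRG half-life and clearance tables could then be nearly empty, or filled by an unrepresentative subset with distorted areas. The SAP names no fallback and does not ask for the selection to be described.

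**Working it through.** **1. The plan's own figure.** Protocol 1.6 says Day 99 is more than four half-lives of human IgG, and Day 121 more than five. At 21 days: (99 − 1)/21 = 4.67 and (121 − 1)/21 = 5.71. Both statements reproduce. The fraction left at Day 99 is 2^(−4.67) = 3.9%, so whether it is quantifiable depends on the assay limit.

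**2. Count of eligible terminal points.** The count applies separately to CTB011 and CTB012. Samples after Tmax:

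| Day 99 value | Tmax Day 4 | Tmax Day 8 | Tmax Day 15 |
|---|---|---|---|
| BLQ, set to missing | 2 (Days 8, 15) | 1 (Day 15) | 0 |
| Quantifiable | 3 (Days 8, 15, 99) | 2 (Days 15, 99) | 1 (Day 99) |

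Three points arise in one cell only. This step needs no assumption.

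**3. The 20% rule as a second block.** Assume one compartment with first-order absorption, C(t) ∝ ka/(ka − k) × [exp(−k t) − exp(−ka t)], with k = ln 2 / half-life and ka 0.5 to 1.0 per day. Use the SAP's linear trapezoid, with Day 15 (t = 14) as the last quantifiable sample. Extrapolated share = (C_last/k) / (AUC1-t + C_last/k):

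| Assumed half-life (days) | Share beyond Day 15 |
|---|---|
| 14 | 54–57% |
| 17 | 61–63% |
| 21 | 67–68% |
| 28 | 74–75% |

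Every value is far above 20%. AUC1-t to Day 15 would hold only about 25% to 46% of the total (1 − 0.75 to 1 − 0.54).

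**4. Distortion where Day 99 is quantifiable.** The trapezoid then spans 84 days in one step. At 21 days, C99/C15 = 2^(−84/21) = 1/16. The linear area is 84 × (1 + 1/16)/2 = 44.6 × C15; the true area is (1 − 1/16)/k = 28.4 × C15. The segment is overstated by 44.6/28.4 − 1 = 57%. Over the whole curve, AUC1-inf is 1.33 to 1.34 times its true value at 21 days, 1.56 to 1.60 at 14 days and 1.20 to 1.21 at 28 days. CL/F is Dose/AUC1-inf, so it falls to between 1/1.60 = 0.62 and 1/1.20 = 0.83 of its true value.

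**5. Who is retained: illustration only.** Assumptions: half-life CV 25%, exposure CV 30%, median ka 0.7 per day (CV 40%), residual CV 15%, assay limit 2%, 5% or 10% of the typical dose/V. Each cell gives the percentage keeping λz, then their median true half-life in days:

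| Population median half-life | Limit 2% | Limit 5% | Limit 10% |
|---|---|---|---|
| 14 | 9.9%; 18.7 | 1.6%; 22.5 | 0.2%; 26.2 |
| 17 | 21.7%; 19.9 | 5.9%; 23.7 | 1.0%; 27.6 |
| 21 | 32.6%; 22.0 | 15.4%; 25.2 | 4.3%; 29.5 |

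The retained median exceeds the population median in every cell. Median exposure among those retained is 1.04 to 1.40 times typical, so exposure selects as well.

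**6. Can the LRG supply these parameters?** The sources conflict. Protocol Table 3-1 and Appendix C give LRG SYN023 samples to Day 43 and then Day 99. SAP 10.2 and Protocol Appendix D list Day 71 and later days, with none at Day 99. SAP 15.1.1 splits the sampling by protocol version. On either list λz is usually reachable: with data only to Day 43 there are 4 points if Tmax is Day 4 and 3 if it is Day 8. AUC1-inf is less secure. With Day 43 last, the step 3 formula gives an extrapolated share of 19–20% at 17 days, 26–27% at 21 days and 33% at 25 days. This can breach the 20% limit.

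**The case against.** The plan qualifies these parameters more than once, and sparse NRG sampling is deliberate. Protocol 3.13 speaks of selected time points, Protocol 2.2.6 asks the NRG only to contribute to the pharmacokinetic description, and Protocol 3.4.1 makes pharmacodynamics and pharmacokinetics the main purpose of the LRG. A reader might infer that the NRG pharmacokinetic objective cannot be met at all. The documents do not support that: Cmax, Tmax and AUC1-t remain computable, and the objective is descriptive.

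A reader might also infer that almost none of the 184 NRG SYN023 recipients would have terminal parameters. That follows only if the non-detectability sentence is taken at face value. It appears without a reference in a rationale for avoiding pregnancy, and Protocol 7.3 is weaker. In the illustration, retention runs from 0.2% to 32.6%, which is 0.002 × 184 ≈ 0 to 0.326 × 184 ≈ 60 subjects.

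The two harms also trade off. Where most subjects pass, the selection is mild (22.0 against 21 days); where it is strong (26.2 against 14 days), few values remain. Nor is a formal LRG–NRG comparison planned, and the reported n would show depletion.

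All of this stands, and it limits the size of the point. It does not answer the count in step 2 or the area inflation in step 4. A reported n does not show why subjects dropped out.

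**Conclusion.** The point holds for the λz-dependent NRG parameters. It is exact, and free of pharmacokinetic assumptions, that a BLQ Day 99 value makes λz, half-life, AUC1-inf, CL/F and Vd/F inestimable for that subject, and that otherwise they need Tmax on Day 4. The protocol's own expectation is that Day 99 will be undetectable.

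The sizes are conditional. The 54% to 75% extrapolation beyond Day 15 and the 20% to 60% inflation of AUC1-inf rest on an assumed one-compartment model and half-lives of 14 to 28 days. The 0.2% to 33% retention also rests on assumed variability and assay limits. It would go too far to say that only slow eliminators are kept, since higher exposure selects too. AUC1-t would end at Day 15 in some NRG subjects and Day 99 in others under one label.

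This affects part of one descriptive secondary objective. No hypothesis test, power figure or primary endpoint element is touched. It should be settled before unblinding so that the choice is not driven by the data.

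**What to change.** - In SAP 10.3, for the NRG, report concentrations by day, observed Cmax and Tmax, and a partial AUC to Day 15. Do not summarise individual non-compartmental half-life, AUC1-inf, CL/F or Vd/F.
- Estimate those parameters from a population PK model on pooled LRG and NRG concentrations, with BLQ values handled as censored.
- Reconcile the LRG sampling days across Protocol Table 3-1, Appendices C and D, and SAP 10.2 and 15.1.1. Rely on LRG non-compartmental terminal parameters only after that. If Day 71 was not assayed and Day 99 is BLQ, the LRG can fail the 20% rule too.
- Wherever λz is attempted, report how many subjects kept it and why the others did not.
- Align the wording of the pharmacokinetic objective with these changes.

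The cost is SAP and objective wording plus modest modelling work. No new samples or visits are needed.

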11.1. Handling Missing Data

Concentrations that are below the limit of quantification (BLQ) will be treated as zero for descriptive statistics. Mean BLQ concentrations will be presented as BLQ, and the SD and coefficient of variation (CV) will be reported as not applicable. Missing concentrations will be excluded from the calculation.

11.2. Pharmacodynamic Concentrations

Blood samples will be obtained during the course of the study for use in determining the concentration of RVNA in serum. These will be collected before administration of Study Drug on Day 1, before administration of vaccination on Days 4, 8, 15, and 29, and Days 43, 71, 99, 127, 155, 183, 274, and 365.

Individual serum concentrations of RVNA will be presented in the data listings and summarized by nominal time point for ease of presentation using descriptive statistics (n, mean, SD, CV, min, median, and max), by ADA status, and also by Per-protocol (LRG and NRG) and As-treated

Populations. The mean serum concentrations of RVNA will be plotted versus nominal collection time, and the individual serum concentrations of RVNA will be plotted versus actual collection time on both linear and semilogarithmic scales, by ADA status.

11.3. Pharmacodynamic Parameters

The serum concentration-time data for RVNA will be analyzed by non-compartmental analysis using WinNonlin Phoenix Version 8.0 or higher. For PD analysis, actual sampling times and actual doses administered will be used. For the calculation of PD parameters, all serum concentrations that are BLQ prior to the first measurable concentration will be set to zero. The BLQ values that are between measurable concentrations will be set to missing. The BLQ values that occur at the end of the profile after the last quantifiable concentration will be set to missing.

If data allow, the following PD parameter will be derived from the individual serum concentrations of RVNA over time profile using non-compartmental methods:

AUEC₁₋₁₅ Area under the effect-time curve from time 0 on Study Day 1 to Study Day 15
 calculated using the linear trapezoidal linear interpolation rule

Individual serum PD parameters of RVNA will be presented in the data listings. Further, RVNA PD parameters will be summarized using descriptive statistics (*n*, mean, SD, CV, min, median, and max) by ADA status, and also by Per-protocol (LRG and NRG) and As-treated Populations.

12. Immunology Laboratory other than PK and PD

As part of the secondary objectives of the study, all immunogenicity analyses will be based on per-protocol and as-treated subjects who received at least one dose of study drug. The presence and effect of anti-SY023 antibodies (anti-CTB011, anti-CTB012) will be evaluated.

Immunogenicity will be summarized for initial LRG subjects, general LRG subjects and NRG subjects, separately. The summary will take forms of GMC or GMT and be based on standard log transformations (Section 15.2) for all time points as collected and as available. If the assay read-out does not occur at the starting dilution – indicating a very low amount of antibodies, below the detection limit of the assay – then the antibody titer for the sample is set to D/2, half of the starting dilution. No imputation for missing data will be performed. Data will be transformed as appropriate prior to analysis. GM, Geo SD and 95% CI will be provided in summary tables. Inferential testing will not be performed. In case of pre-vaccination immunogenicity levels are not zero, GM fold increase will be presented as the alternative statistics to GMC or GMT. Let v_{pre} be a subject's pre-vaccination (baseline) immunogenicity value and v_{post} be the post-vaccination value, then the fold increase is

$$f_i = v_{post}/v_{pre}.$$

Fold increases express intra-individual relative increases in immunogenicity values. Just like immunogenicity values, log transformed fold increases tend to be normally distributed, and for the statistical analysis of fold increases the methods described for the analysis of immunogenicity values can be used.

13. Interim Analysis

Not applicable. Regarding summaries planned for DSMB meetings, please refer to a standalone DSMB Charter.

14. Changes in the Planned Analysis

Not applicable in this version.

15. Appendices

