1 INTRODUCTION

1.1 Background

Rabies is an acute lethal viral disease transmitted from animals to humans. Rabies is present in more than 150 countries and territories and on every continent except Antarctica. All mammals are believed to be susceptible to infection with the rabies virus. In the US, multiple rabies virus variants are maintained in wild mammalian reservoir populations such as raccoons, skunks, foxes, and bats. Infected domestic and wild animals spread rabies to humans via bites or scratches (WHO 2017). Although the US has been declared free of canine rabies virus variant transmission, in developing countries, the primary route of transmission to humans is via the bite of a rabid dog (Manning et al. 2008). There are currently no known effective rabies antiviral drugs.

Once the clinical signs of rabies manifest, the mortality rate approaches 100%. Therefore, PEP against rabies infection is of critical importance. Rabies vaccination alone is used for pre-exposure prophylaxis (Immunization Practices Advisory Committee 1980). Studies on the development of rabies virus neutralizing activity through immunization indicate that on Day 7 post vaccination most individuals lack adequate rabies virus neutralizing activity while by Day 14 after immunization virtually all individuals vaccinated with a modern rabies vaccine have adequate rabies neutralizing activity (Grandien et al.1977, Vodopija et al.1988a)

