7.8 Sample Size Considerations Primary Objective: Composite Endpoint Element

Since the primary objective is composite multiple endpoints will be determined. Each endpoint will have different requirements on the Study sample size determination. The contribution of various endpoints to sample size is tabulated in Table 7.8-1. The specific analyses are discussed in Sections 7.81 - .

Table 7.8-1 Sample Size Estimates for Pharmacodynamic Endpoints (all 80% power, alpha ≤0.025)

CONFIDENTIAL

RVNA GMC	Priority	Sample Size total 1:1	Mean ratio SYN/HRIG	Margin	CI	CV %
Superiority Study Day 8	Primary	<10	>10.0	10%	95	16.11
Non inferiority Study Day 99 GMC	Primary	138	0.88	20%	95	17.00
Non inferiority Study Day 99 percent subjects ≥ 0.5 IU/mL	Primary	72	1.0	10%	95	NA
Superiority Study Day 3	Secondary	<10	>10.0	10%	95	9.83
Superiority AUEC ₁₋₁₅	Secondary	320	1.45	10%	90	108.78

7.8.1 Superiority of Geometric Mean of RVNA Study Day 8

Superiority test for the ratio of two geometric means is used for determining the sample size. The null hypothesis is that the ratio for the two treatments is less than the defined margin that is expressed as:

$$H_0: \emptyset \leq \emptyset_L \text{ where } \emptyset_L > 1$$

Where, $\emptyset = \frac{GM_{SYN023}}{GM_{HRIG}}$; GM is the geometric mean.

The alternative hypothesis for superiority is expressed as: $H_1: \emptyset > \emptyset_L$. The ratio of superiority is more than ten-fold. The sample size required for this comparison is less than 10.

7.8.2 Non-inferiority of Geometric Serum RVNA on Study Day 99

The timepoint selected for non-inferiority in the current trial is based on need for a “later” timepoint at which to evaluate vaccine immunogenicity is from historical data from protocol SYN023-002 for which there are Study Day 84 and Study Day 112 timepoint (Table 7.8.2-1). The Study Day 99 is selected as being between these timepoints and closest for estimation.

The 20% margin was selected since it is a recommended bioequivalence margin for a lower bound of 0.8 (FDA 2001). Applying this margin to historical data near the Study Day 99 timepoint shows RVNA concentrations both well above the 0.5 IU/mL and should provide protective concentration in all subjects (Table 7.8.2-1).

Table 7.8.2-1 RVNA Historical Values by Timepoint for SYN023-002 Protocol

Visit	SYN023			HRIG		
	N	Geometric Mean	95% CI	N	Geometric Mean	95% CI
Day 42	73	8.05	(6.58, 9.85)	76	9.18	(7.91, 10.66)
Day 84	72	2.33	(1.79, 3.03)	75	2.75	(2.27, 3.33)

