4.3.5. NRG Per-Protocol Population

All subjects who

- are randomized
- receive the correct study drug
- have inclusion/exclusion criteria confirmed

- complete all rabies vaccinations scheduled
- lack major protocol deviations
- have adequate wound treatment and study drug injection of all exposure sites
- are not part of the LRG enrollment

will be included in the “Per-protocol” Population. Initial exclusion criteria that must be confirmed are the species of the biting animal; a high-risk exposure (WHO Category 3); interval ≤ 54 hours from the bite to the start of prophylaxis; the absence of RVNA ≥ 0.1 IU in serum obtained at Study Day 1, time “0” blood collection (WHO, 2013). Subjects who are discovered to not have satisfied criteria for the Per-protocol Population may be excluded from that population by the Per-protocol Adjudication Board.

5. Subject Disposition

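### SAP 11.3 drops a Day 8 RVNA that is below quantification between measurable Day 4 and Day 15 values, which inflates that subject's AUEC1-15 about 1.5- to 1.6-fold, probably only in the HRIG arm

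*SAP*

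**What the plan says.** SAP 11.3 derives AUEC1-15 from each subject's RVNA profile, "calculated using the linear trapezoidal linear interpolation rule". Before that step, "all serum concentrations that are BLQ prior to the first measurable concentration will be set to zero", and "The BLQ values that are between measurable concentrations will be set to missing". These are the rules that SAP 10.3 gives for the serum concentrations of the two monoclonal antibodies.

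RVNA is drawn before Study Drug on Day 1 and then "before administration of vaccination on Days 4, 8, 15, and 29" (SAP 11.2). Only Days 1, 4, 8 and 15 fall within the AUEC window.

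No other rule overrides this one:

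- SAP 11.1 says "Concentrations that are below the limit of quantification (BLQ) will be treated as zero for descriptive statistics", which does not reach the AUEC.
- The half-of-starting-dilution rule in SAP 12 is for immunology other than PK and PD.
- Protocol 3.9.2 only classifies a low or missing value as protective when it is flanked by protective ones.

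AUEC1-15 is a secondary endpoint tested for superiority (SAP 8.2). It sets the requirement of 320 per-protocol subjects (Protocol 7.8.4, SAP 4.1).

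**The concern.** Dropping an interior BLQ value can be reasonable for a drug concentration that is only declining. RVNA in this trial comes from two sources, passive antibody first and vaccine response later. Protocol 1.1 says that "on Day 7 post vaccination most individuals lack adequate rabies virus neutralizing activity while by Day 14" virtually all have it. Most of the area up to Day 15 is therefore the late rise. If a BLQ Day 8 result is deleted, the subject is credited with a share of the Day 15 response on days when the assay found nothing quantifiable.

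The rule also depends on what happened on Day 4. If Day 4 is BLQ too, both values are leading values and become zero, which gives the smaller area. If Day 4 is barely measurable, Day 8 disappears and the area jumps.

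The effect is unlikely to be balanced between arms. On Day 8 the protocol expects a large separation ("The ratio of superiority is more than ten-fold"), so values near the quantification limit should come from HRIG recipients. Inflating their AUEC would understate the early difference that the endpoint is meant to measure.

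**Working it through.** **Plan's own figure.** Inputs from Protocol 7.8.4: ratio 1.45, superiority bound 1.10, CV 108.78%, one-sided alpha 0.025, power 80%.

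- SD on the log scale = √ln(1 + 1.0878²) = 0.8837
- Difference = ln(1.45/1.10) = 0.2763
- n per arm = 2 × (1.96 + 0.8416)² × 0.8837² / 0.2763² ≈ 161, or 322 in total against 320 stated
- Power with 160 per arm = 79.8%

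The stated size reproduces.

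**One subject.** Elapsed days are 0, 3, 7 and 14. Day 1 is taken as 0, since per-protocol subjects need "the absence of RVNA ≥ 0.1 IU in serum obtained at Study Day 1". C4, C8 and C15 are the RVNA values on Study Days 4, 8 and 15.

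- Day 8 kept: 1.5·C4 + 2·(C4 + C8) + 3.5·(C8 + C15)
- Day 8 deleted: 1.5·C4 + 5.5·(C4 + C15)

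When C15 dominates, the ratio tends to 5.5/3.5 = 11/7 = 1.57.

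The documents give no LLOQ and no Day 15 level, so the values below are assumed (IU/mL).

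| C4 | Day 8 value if kept | C15 | Kept | Deleted | Ratio |
|---|---|---|---|---|---|
| 0.15 | 0.05 | 5 | 18.30 | 28.55 | 1.56 |
| 0.10 | 0 | 5 | 17.85 | 28.20 | 1.58 |
| 0.10 | 0.05 (LLOQ/2 for LLOQ 0.1) | 5 | 18.13 | 28.20 | 1.56 |

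With LLOQ 0.05 to 0.2, C4 at 1 to 4 times the LLOQ, C15 of 5 or more, and Day 8 replaced by 0, LLOQ/2 or LLOQ, the ratio runs from 1.50 to 1.63. With C15 as low as 0.5 the range widens to 1.17 to 1.84.

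**Discontinuity.** At C15 = 5, BLQ on Days 1, 4 and 8 gives 3.5 × 5 = 17.5. With 0.1 on Day 4 and Day 8 still BLQ, the area is 28.2, a 61% jump for a trivial difference.

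**Day 4.** A BLQ Day 4 after a BLQ Day 1 is set to zero and stays in the profile. If Day 1 was measurable, deleting Day 4 alone changes the area by only about 1% to 2% (Day 1 about 0.1, Day 8 0.15, Day 15 5 or 10). The problem is therefore specific to Day 8.

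**Which arm.** Protocol Table 7.8.3-1 gives the numbers at or above 0.5 IU/mL:

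| | SYN023 | HRIG |
|---|---|---|
| Day 3 (Study Day 4) | 74/75 | 1/76 |
| Day 7 (Study Day 8) | 75/75 | 6/76 |

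For SYN023, 0/75 below 0.5 at Day 7 has a one-sided 95% upper bound of 1 − 0.05^(1/75) = 3.9%, and the BLQ share can only be lower if the LLOQ is below 0.5.

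**Group effect.** If a share f of HRIG subjects is affected, the HRIG geometric mean rises by (11/7)^f. The values of f are assumed. Power is for 160 per arm and a true ratio of 1.45.

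| f | HRIG geometric mean | Expected ratio | Power vs 1.10 | Power vs 1.0 |
|---|---|---|---|---|
| 0 | ×1.000 | 1.45 | 79.8% | 96% |
| 1% | ×1.005 | 1.44 | 78.5% | 96% |
| 5% | ×1.023 | 1.42 | 72.8% | 94% |
| 10% | ×1.046 | 1.39 | 64.8% | 91% |
| 20% | ×1.095 | 1.33 | 46.9% | 81% |

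**The case against.** The best defence is that the pattern may be rare. A reader might infer that HRIG recipients dip to a trough around Day 8, but the documents do not show one. The HRIG count at or above 0.5 IU/mL rises, from 1/76 to 6/76. With the half-life of about 21 days in Protocol 1.1, elimination over four days removes only 1 − 2^(−4/21) = 12%, while vaccine antibody is starting to appear. A measurable Day 4 followed by a BLQ Day 8 therefore needs a Day 4 value close to the LLOQ, or assay noise. The Protocol 1.1 statement about Day 7 concerns adequacy; it does not say that values are unquantifiable. Being below 0.5 is not the same as being BLQ, so the 70/76 HRIG subjects below 0.5 at Day 7 do not supply a frequency. This objection stands, and it is why the table starts at 1%, where the loss is negligible.

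Three further points limit the consequence:

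- The larger power losses are against the protocol's 1.10 bound. SAP 8.2 states no margin and refers to 8.1.1.1 for presentation, where superiority means a ratio above 1. If 1.0 is the bound, power stays above 80% even at 20% affected.
- Protocol 7.8.4 does not say how BLQ values were handled in the planning estimate of 147.55%. If the same rule was used, 1.45 already contains the effect.
- The endpoint is secondary, and the bias runs against SYN023.

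None of this defends the rule for a subject it does affect. SAP 11.3 derives the AUEC only where data allow, but it does not define that condition, so it cannot be relied on to exclude such profiles.

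**Conclusion.** The rule is wrong as written for RVNA. A subject with Day 4 measurable, Day 8 BLQ and a Day 15 response well above the LLOQ gets an AUEC1-15 about 1.5 to 1.6 times too large (roughly 1.2 to 1.8 if the Day 15 response is weak), and the score jumps on a trivial Day 4 difference.

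That it would affect only HRIG subjects is a reasonable inference from the earlier trial, but not a demonstrated fact. In that case the SYN023/HRIG ratio is pulled down: power is lost and the estimate is biased, but type I error is not inflated. No primary element uses this calculation.

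Two stronger readings are tempting and are not supported. One is that the trial will lose a large part of its AUEC power: that depends entirely on assumed frequencies, on the 1.10 bound, and on the planning ratio not having been computed with the same rule. The other is that the artefact outweighs the planned treatment effect because 1.57 exceeds 1.45: the first is a single-subject factor and the second a ratio of group geometric means. The matching group effect is 1.005 to 1.095 for 1% to 20% affected.

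**What to change.** In SAP 11.3, replace the BLQ rule for RVNA with one that covers AUEC1-15:

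- Keep every BLQ result on Days 4 and 8 at its visit, with one prespecified substitution, whether it falls before or between measurable values. Zero or LLOQ/2 would both remove the jump; use the other as a sensitivity analysis.
- State the LLOQ of the RVNA assay.
- Treat as missing only samples that were not drawn or could not be assayed.

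The cost is a short SAP change and a setting in the non-compartmental software. It needs no new data or subjects, and it should be made before unblinding.
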